## 12.7 Analysis of Primary Endpoint

An assessment of the null and alternative hypotheses from Section 12.3,

$$H_0: \pi_{\text{NIRTRAKS}} \geq 34.8\%$$

$$H_A: \pi_{\text{NIRTRAKS}} < 34.8\%$$

will be carried out using the exact test of the binomial distribution at the 1-sided 0.05 level of significance on ITT subjects who experienced the primary endpoint or who had follow-up within 1 month (the allowable window for the 3-year contact) of 3-years post-procedure. If this upper interval is below 34.8%, the null hypothesis above will be rejected in favor of the alternative (the results of the exact confidence interval approach will yield the same conclusion as the 1-sided exact test of the null hypothesis). In addition, the assessment of the hypotheses will be carried out on all ITT subjects by (a) comparing the 1-sided upper 95% confidence interval of the Kaplan-Meier estimate of the primary endpoint rate to 34.8%; subjects not experiencing the endpoint will be censored at 3 years post-procedure or day of withdrawal, whichever is earlier; and (b) multiply imputing the primary endpoint incidence for subjects prematurely withdrawing prior to 3 years minus 1 month post-procedure and prior to experiencing the primary endpoint, followed by a test of hypothesis on the imputed data (see details in Section 12.8 below). The results of the various ITT analyses on the primary endpoint will be compared descriptively to assess the sensitivity of results to missing data.

Finally, the analysis will be carried out on the PP population (secondary analysis) using the exact test of the binomial distribution and an exact 1-sided upper 95% confidence interval.

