## 12.8 Handling of Missing Data in the Analysis of the Primary Endpoint

The primary analysis set will be the ITT population, which includes all subjects enrolled into the study. Subjects who prematurely withdraw prior to the 3-year (minus the allowable 1-month window) contact and prior to experiencing the primary endpoint will have their missing primary endpoint result handled using the following 3 approaches; results will be compared across the 3 approaches for consistency:

1. Only subjects with appropriate follow up (at least 3 years minus 1 month) or who experienced the primary endpoint by 3 years will be included in the exact hypothesis testing, as discussed above. This is the primary analysis..
2. Multiple imputation: This will be used to impute primary endpoint status (yes/no) for subjects with missing primary endpoint data. The logistic regression approach to multiple imputation will be carried out using SAS PROC MI. The covariates to be used in the imputation model will be age, sex, prevalence of diabetes, target lesion length and reference vessel diameter. Five data sets will be imputed, and a 1-sided test of the above null hypothesis will be carried out on each data set using the normal approximation to the binomial distribution. SAS PROC MIANALYZE on the results of the 5 significance tests will then be used to obtain an overall assessment of the significance of the 1-sided test across the 5 data sets.
3. As a third analysis and as discussed above, the Kaplan-Meier estimate of the 3-year primary endpoint rate, and its 1-sided upper 95% confidence interval will be calculated. Subjects not experiencing the primary endpoint within 3 years will be

censored at 3 years or the date of withdrawal from the study, whichever is earlier. The upper confidence limit will be compared to 34.8%; if less than 34.8%, the primary endpoint rate will be considered to be significantly less than the performance goal in this analysis.

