4.2.2 Per-Protocol

Per-protocol (PP) analysis will also be conducted. Per-protocol is defined as all subjects who sufficiently comply with the study protocol. Compliance covers treatment received, availability of follow-up data (follow-up of at least 3 years, allowing for a visit window of 3 years \pm 1 month), and absence of major protocol deviations.

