4.3.2 Analysis of Primary Endpoint

The primary endpoint for this study is TVF, which is defined as a composite of cardiac death, target vessel MI, or clinically driven TVR by percutaneous or surgical methods within 3 years post-procedure.

No formal statistical test will be performed, as this study is descriptive only. The TVF rate at 3 years and the exact two-sided 95% confidence intervals will be provided. In addition, the TVF at 3 years will be estimated for all ITT subjects by generating the two-sided 95% confidence

interval of the Kaplan-Meier estimate of the primary endpoint rate; subjects not experiencing the endpoint will be censored at 3 years post-procedure or day of withdrawal, whichever is earlier. Finally, the same analysis will be carried out on the PP population (secondary analysis).

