4.3.3 Analysis of Secondary Endpoints

All secondary endpoints (listed below) are dichotomous variables. Secondary endpoints will be presented as the number and percentage of subjects experiencing the outcome, along with two-sided exact 95% confidence intervals of the percentages. Included in the denominators for each outcome will be patients experiencing the event within the period (e.g., 30 days for 30-day time point, 270 days for 9-month time point, 365 days for 1-year time point, 730 days for 2-year time point, and 1095 days for 3-year time point) or who have adequate follow-up (e.g., at least 16 days for 1-month time point, at least 240 days for the 9-month time point, at least 335 days for the 1-year time point, at least 700 days for 2-year time point, and at least 1065 days for 3-year time point).

In addition, a Kaplan-Meier (K-M) estimate of the event-free survival rate and its corresponding standard error will be presented for cardiac death, target vessel MI, clinically driven TLR and TVR, with a corresponding K-M curve.

The secondary endpoints that will be reported are as follows:

1. **TVF** at 9 Months.
2. **All cause death** at 30 days, and 1, 2 and 3 years.
3. **Cardiac death** at 30 days, and 1, 2 and 3 years.
4. **All cause MI** at 30 days, and 1, 2 and 3 years.
5. **Target vessel MI** at 30 days, and 1, 2 and 3 years.
6. **Clinically driven TLR** at 30 days, and 1, 2 and 3 years.
7. **Clinically driven TVR** at 30 days, and 1, 2 and 3 years.
8. **Acute success rates**

Device success: Attainment of <50% final residual stenosis of the target lesion using the NIRxcell Stent System only.

Lesion success: Attainment of <50% final residual stenosis of the target lesion using any percutaneous method.

Procedure success: Attainment of <50% residual stenosis of the target lesion and no in-hospital death, MI or TLR.

9. **Stent thrombosis** at hospital discharge, at 30 days, and 1, 2 and 3 years.

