4.4 Adverse Events

A Treatment Emergent Adverse Event (TEAE) is an event that emerges, or a pre-existing event that worsens, any time during or after stent implantation. Adverse events will be coded by the MedDRA system version 18.1 or later. The per-event and per-patient incidence of TEAEs will be presented overall and by MedDRA system organ class and preferred term. This will be repeated for serious TEAEs.

5 TABLES, FIGURES, and LISTINGS

Table 1.1a Primary Endpoints – Intention-to-Treat Analysis Set

Primary Endpoint	ITT Subjects with Available Data (N=xx subjects)	Two-sided Binomial Exact 95% CI
TVF at 3 years	xx.xx% (xx/xx)	[xx.xx%, xx.xx%]
Cardiac Death	xx.xx% (xx/xx)	[xx.xx%, xx.xx%]
Target Vessel MI	xx.xx% (xx/xx)	[xx.xx%, xx.xx%]
Clinically-driven TVR	xx.xx% (xx/xx)	[xx.xx%, xx.xx%]

Note: Events defined for the period of 3 year post-procedure follow up are reported for patients with at least 1050 days of follow-up or with event to 3 years (1080 days).

Table 1.1b Primary Endpoints – Per-Protocol Analysis Set

Table 1.2 Secondary Endpoints – Intention-to-Treat Analysis Set

	ITT Subjects (N=xx subjects)	Two-sided Binomial Exact 95% CI
TVF at 9 months	xx.xx% (xx/xx)	[xx.xx%, xx.xx%]
All Cause Death		
30-day	xx.xx% (xx/xx)	[xx.xx%, xx.xx%]
1-year	xx.xx% (xx/xx)	[xx.xx%, xx.xx%]
2-year	xx.xx% (xx/xx)	[xx.xx%, xx.xx%]
3-year	xx.xx% (xx/xx)	[xx.xx%, xx.xx%]
Cardiac Death		
30-day	xx.xx% (xx/xx)	[xx.xx%, xx.xx%]
1-year	xx.xx% (xx/xx)	[xx.xx%, xx.xx%]
2-year	xx.xx% (xx/xx)	[xx.xx%, xx.xx%]
3-year	xx.xx% (xx/xx)	[xx.xx%, xx.xx%]
All Cause MI		
30-day	xx.xx% (xx/xx)	[xx.xx%, xx.xx%]
1-year	xx.xx% (xx/xx)	[xx.xx%, xx.xx%]
2-year	xx.xx% (xx/xx)	[xx.xx%, xx.xx%]
3-year	xx.xx% (xx/xx)	[xx.xx%, xx.xx%]
Target Vessel MI		
30-day	xx.xx% (xx/xx)	[xx.xx%, xx.xx%]
1-year	xx.xx% (xx/xx)	[xx.xx%, xx.xx%]
2-year	xx.xx% (xx/xx)	[xx.xx%, xx.xx%]
3-year	xx.xx% (xx/xx)	[xx.xx%, xx.xx%]
Clinically-driven TLR		
30-day	xx.xx% (xx/xx)	[xx.xx%, xx.xx%]
1-year	xx.xx% (xx/xx)	[xx.xx%, xx.xx%]
2-year	xx.xx% (xx/xx)	[xx.xx%, xx.xx%]
3-year	xx.xx% (xx/xx)	[xx.xx%, xx.xx%]
Clinically-driven TVR		
30-day	xx.xx% (xx/xx)	[xx.xx%, xx.xx%]

1-year	xx.xx% (xx/xx)	[xx.xx%, xx.xx%]
2-year	xx.xx% (xx/xx)	[xx.xx%, xx.xx%]
3-year	xx.xx% (xx/xx)	[xx.xx%, xx.xx%]
Device Success ¹	xx.xx% (xx/xx)	[xx.xx%, xx.xx%]
Lesion Success ²	xx.xx% (xx/xx)	[xx.xx%, xx.xx%]
Procedure Success ³	xx.xx% (xx/xx)	[xx.xx%, xx.xx%]
Stent Thrombosis		
Discharge	xx.xx% (xx/xx)	[xx.xx%, xx.xx%]

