30-day	xx.xx% (xx/xx)	[xx.xx%, xx.xx%]
1-year	xx.xx% (xx/xx)	[xx.xx%, xx.xx%]
2-year	xx.xx% (xx/xx)	[xx.xx%, xx.xx%]
3-year	xx.xx% (xx/xx)	[xx.xx%, xx.xx%]

1 Device success is defined as attainment of <50% final residual stenosis of the target lesion using only the NIRxcell Stent System.

2 Lesion success is defined as attainment of <50% final residual stenosis of the target lesion using any percutaneous method.

3 Procedure success is defined as attainment of <50% residual stenosis of the target lesion and no in-hospital death, MI, or TLR.

Events in this table have been adjudicated by the CEC.

Denominators for 30-day events will reflect the number of patients with an adjudicated event in 30 days or follow-up through 16 days.

Denominators for 9-month events will reflect the number of patients with an adjudicated event in 270 days or follow-up through 240 days.

Denominators for 1-year events will reflect the number of patients with an adjudicated event in 365 days or follow-up through 335 days.

Denominators for 2-year events will reflect the number of patients with an adjudicated event in 730 days or follow-up through 700 days.

Denominators for 3-year events will reflect the number of patients with an adjudicated event in 1095 days or follow-up through 1065 days.

Table 2 Enrollment by Site

Site	Site Name	Site Location	ITT Subjects (N=xx subjects)	Per Protocol Subjects (N=xx subjects)
001			xx	xx
002			xx	xx
Total			xx	xx

Table 3 Compliance Table -- Intention-to-Treat Analysis Set

Site	Index Procedure Form	30-Day Contact ¹	9-Month Contact ²	1-Year Contact ³	2-Year Contact ⁴	3-Year Contact ⁵
	(received/expected, %)	(received/expected, %)	(received/expected, %)	(received/expected, %)	(received/expected, %)	(received/expected, %)
001	xx.xx% (xx/xx)	xx.xx% (xx/xx)	xx.xx% (xx/xx)	xx.xx% (xx/xx)	xx.xx% (xx/xx)	xx.xx% (xx/xx)
002	xx.xx% (xx/xx)	xx.xx% (xx/xx)	xx.xx% (xx/xx)	xx.xx% (xx/xx)	xx.xx% (xx/xx)	xx.xx% (xx/xx)
...
014						
015						
Total	xx.xx% (xx/xx)	xx.xx% (xx/xx)	xx.xx% (xx/xx)	xx.xx% (xx/xx)	xx.xx% (xx/xx)	xx.xx% (xx/xx)

1 Denominator for 30-Day contact includes patients who had 30-day visit form filled or patients who have reached 44 (30+14) days after procedure (data export date - procedure date) and excludes patients who died or withdrew before 44 days.

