2 Denominator for 9-Month contact includes patients who had 9-month visit form filled or patients who have reached 300 (270+30) days after procedure (data export date - procedure date) and excludes patients who died or withdrew before 300 days.

3 Denominator for 1-year contact includes patients who had 1-year visit form filled or patients who have reached 395 (365+30) days after procedure (data export date - procedure date) and excludes patients who died or withdrew before 395 days.

4 Denominator for 2-year contact includes patients who had 2-year visit form filled or patients who have reached 760 (730+30) days after procedure (data export date - procedure date) and excludes patients who died or withdrew before 760 days.

5 Denominator for 3-year contact includes patients who had 3-year visit form filled or patients who have reached 1125 (1095+30) days after procedure (data export date - procedure date) and excludes patients who died or withdrew before 1125 days.

Table 4 Patient Disposition

	ITT Subjects (N=xx subjects)	Per Protocol Subjects (N=xx subjects)
	n (%)	n (%)
Enrolled	xx (xx.xx%)	xx (xx.xx%)
Completed the study	xx (xx.xx%)	xx (xx.xx%)
Not completed all required follow-up visits	xx (xx.xx%)	xx (xx.xx%)
Primary reason for not completed		
Withdrew consent	xx (xx.xx%)	xx (xx.xx%)
Lost to follow-up	xx (xx.xx%)	xx (xx.xx%)
Adverse event	xx (xx.xx%)	xx (xx.xx%)
Death	xx (xx.xx%)	xx (xx.xx%)
Lack of efficacy	xx (xx.xx%)	xx (xx.xx%)
Protocol violation	xx (xx.xx%)	xx (xx.xx%)
Physician decision	xx (xx.xx%)	xx (xx.xx%)
Study cancelled	xx (xx.xx%)	xx (xx.xx%)
Other	xx (xx.xx%)	xx (xx.xx%)

Table 5 Demographic and Medical History – Intention-to-Treat Analysis Set

Characteristics	ITT Subjects (N=xx subjects)	95% CI
Demographics		
Age (yrs)		
Mean±SD (N)	xx.xx±xx.xx (xx)	[xx.xx, xx.xx]
Median (Q1, Q3)	xx.xx (xx.xx, xx.xx)	
Range (min, max)	(xx.xx, xx.xx)	
Male	xx.xx% (xx/xx)	[xx.xx%, xx.xx%]
Ethnicity		
Hispanic or Latino	xx.xx% (xx/xx)	[xx.xx%, xx.xx%]
Not Hispanic or Latino	xx.xx% (xx/xx)	[xx.xx%, xx.xx%]
Race		
American Indian or Alaska Native	xx.xx% (xx/xx)	[xx.xx%, xx.xx%]
Asian	xx.xx% (xx/xx)	[xx.xx%, xx.xx%]
Black or African American	xx.xx% (xx/xx)	[xx.xx%, xx.xx%]
Native Hawaiian or Other Pacific Islander	xx.xx% (xx/xx)	[xx.xx%, xx.xx%]
White	xx.xx% (xx/xx)	[xx.xx%, xx.xx%]
Other	xx.xx% (xx/xx)	[xx.xx%, xx.xx%]
Medical History/Risk Factor		
Previous MI	xx.xx% (xx/xx)	[xx.xx%, xx.xx%]
Previous PCI	xx.xx% (xx/xx)	[xx.xx%, xx.xx%]

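### Minor, wrong as written: the per-protocol set requires about 3 years of follow-up with no exception for subjects who already had a TVF event, so early cardiac deaths drop out of the secondary PP analysis of TVF

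*SAP*

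**What the plan says.** SAP 4.2.2 names three elements of PP compliance: treatment received, follow-up, and no major protocol deviation. On follow-up it reads "Compliance covers treatment received, availability of follow-up data (follow-up of at least 3 years", with a one-month window around the 3-year contact. Protocol 12.4.2 (v1.2) has the same text. Neither adds an alternative for subjects who have had an event.

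SAP 4.3.2 then states that "the same analysis will be carried out on the PP population (secondary analysis". That analysis is the 3-year TVF rate with an exact two-sided 95% CI, plus a Kaplan-Meier estimate with censoring at 3 years or at withdrawal. TVF includes cardiac death (SAP 3.1), and death is listed as a reason for discontinuation (SAP 2.2.4).

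The rules for endpoint denominators do carry an event alternative:

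- Protocol 12.7, ITT primary analysis: "on ITT subjects who experienced the primary endpoint or who had follow-up within 1 month".
- Protocol 12.8, first missing-data approach: "or who experienced the primary endpoint by 3 years will be included in the exact hypothesis testing".
- SAP 4.3.3, secondary endpoints: "Included in the denominators for each outcome will be patients experiencing the event within the period", or those with adequate follow-up.
- SAP Table 1.1a note: events "are reported for patients with at least 1050 days of follow-up or with event to 3 years (1080 days".
- SAP Table 1.2 note, repeated under Table 11a: "Denominators for 3-year events will reflect the number of patients with an adjudicated event in 1095 days or follow-up through 1065 days".

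The PP shells, Tables 1.1b and 11b, are given by title only.

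**The concern.** A subject who dies of a cardiac cause at month 6 has a fully known primary endpoint but cannot reach month 35, and so fails the PP follow-up condition. Membership of the set therefore depends partly on not having had one component of the endpoint. Removing such a subject takes one event from the numerator and one subject from the denominator, which lowers the PP rate.

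The ITT and PP rates will be read side by side. A PP rate below ITT could be taken as an effect of following the protocol when it comes from how the set was defined. If Table 11b mirrors Table 11a, PP death would be zero by construction from 30 days to 2 years, and nearly so at 3 years.

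**Working it through.** **1. Can the denominator notes bring these subjects back?** No. SAP 4.2.2 fixes who is in the set. The event-or-adequate-follow-up rule then picks, within a set, who counts. Even if the Table 1.1a note carries over to Table 1.1b, it acts on a set from which the early deaths are already gone. On the SAP's 1095-day year count the cut-off is 1095 - 30 = 1065 days; the PP text itself gives no day count, so this conversion is mine.

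**2. The plan's own figure.** SAP 4.1 expects about 52 evaluable of 65 at 7.0% loss a year: 65 x 0.93^3 = 52.3. It reproduces.

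**3. Assumed 3-year cardiac death.** Inputs are the cardiac-death rates in Protocol Table 5, leaving out SPIRIT FIRST (0%, n = 25). They are brought to 3 years in two ways: by the formula in Protocol 12.1, factor 0.5 + 1/(n - 1), which the protocol states for composite TVF only, and by spreading deaths evenly, factor 3/n.

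| Trial | Reported | Protocol formula | Even timing |
|---|---|---|---|
| TAXUS I-IV | 3.8% (5 y) | 3.8 x 0.75 = 2.85% | 3.8 x 3/5 = 2.28% |
| SIRIUS | 3.6% (5 y) | 3.6 x 0.75 = 2.70% | 3.6 x 3/5 = 2.16% |
| ENDEAVOR II | 2.24% (4 y) | 2.24 x 0.833 = 1.87% | 2.24 x 3/4 = 1.68% |
| RAVEL | 2.7% (3 y) | 2.7% | 2.7% |

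The range is 1.68-2.85%.

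**4. Number of deaths.** 52 x 0.0168 = 0.87 to 65 x 0.0285 = 1.85. The chance of none is 0.9832^52 = 0.41 to 0.9715^65 = 0.15. Deaths on days 1065-1095 stay in PP; with even timing this cuts the counts by under 3% (1065/1095 = 0.973).

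**5. Effect on the PP rate.** One death removed: 12/52 = 23.1% becomes 11/51 = 21.6% (1.5 points lower); 15/65 = 23.1% becomes 14/64 = 21.9% (1.2 points lower). In expectation, with F = 0.232 (the protocol's expected TVF rate) and c the cardiac-death rate, PP = (F - c)/(1 - c). This gives 21.9% at c = 0.0168 and 20.9% at c = 0.0285. The exact 95% CI at 12/52 is 12.5-36.8%.

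**6. What if only an event clause were added to the PP criterion?** Events would stay whatever happened later, while event-free withdrawals would be removed. Assume 7% yearly loss unrelated to TVF, so h = -ln 0.93, and TVF of 23.2% with one third (even timing) to two thirds (0.5/0.75, Protocol 12.1) occurring in year 1, uniform within year 1 and within years 2-3.

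- Mean retention is 0.9646 over year 1 and 0.8657 over years 2-3.
- TVF seen before withdrawal: 0.232 x (0.9646/3 + 2 x 0.8657/3) = 0.2085, to 0.232 x (2 x 0.9646/3 + 0.8657/3) = 0.2161.
- Event-free completers: 0.768 x 0.93^3 = 0.6177.
- Rate: 0.2085/0.8262 = 25.2% to 0.2161/0.8338 = 25.9%, which is 2.0-2.7 points above 23.2%.

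With 6% loss over 5 years (Protocol 12.3 reports about 94% complete 5-year data in SIRIUS), yearly retention is 0.94^(1/5) = 0.9877 and the same model gives 23.5-23.6%, an error of 0.3-0.4 point.

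**7. Non-fatal TVF followed by withdrawal.** In the 7% model, TVF subjects who later withdraw number 65 x (0.2085 - 0.232 x 0.8044) = 1.4 to 65 x (0.2161 - 0.1866) = 1.9. The non-fatal share of TVF is (0.232 - c)/0.232 = 0.877-0.928, which leaves 1.2-1.8 subjects per 65.

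**The case against.** The strongest case is that the exclusion is not what the plan means. PP asks only for sufficient compliance. SAP Table 3, footnote 5 (a contact-compliance rule, not an endpoint denominator) "excludes patients who died or withdrew before 1125 days" from the expected count, so a death is not a missed contact there. Table 4 gives the PP column rows for death, withdrawn consent and loss to follow-up. The Kaplan-Meier rule carried over to PP censors at withdrawal, which under the strict reading could act only in the last month. Missed follow-ups are minor deviations (Protocol 14.3).

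These points stand as evidence of intent. They do not override an explicit follow-up condition, and leaving membership to unwritten judgement in an unblinded single-arm study would be a reason to write the rule down.

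Some stronger readings are tempting but not supported:

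- *The plan contradicts itself.* The Table 4 rows would be nearly empty, which is not a contradiction, and a PP subject can still have missed a contact.
- *All TVF events leave PP.* A subject with non-fatal TVF who is followed to about month 35 stays.
- *Every lost subject adds bias.* If withdrawal is unrelated to TVF, losing the 1.2-1.8 non-fatal TVF subjects in step 7 widens the gap to Table 1.1a without biasing PP itself; in that case it is Table 1.1a that lies above 23.2%. The protocol also calls 7% a year conservative.
- *Only events are lost.* An event-free subject with 1050-1064 days is in Table 1.1a but short of 1065 days; removing one raises the rate (12/52 to 12/51 = 23.5%).
- *PP deaths will be reported as zero.* That depends on shells given by title only.

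**Conclusion.** The point holds as a minor one. The rule as written gives a wrong result for cardiac deaths before about month 35: their TVF status is known, yet they leave the PP analysis of TVF. The direction of that part is certain (a lower PP rate). The expected size is 1.3-2.3 points (23.2% to 20.9-21.9%), with a 15-41% chance that no such death occurs at all. The size rests on the Table 5 rates, on the two timing assumptions, and on 23.2% as the true TVF rate.

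A reader might infer that the study's main result is compromised. It is not: the ITT rule handles events correctly, PP is secondary, no formal test is planned, and the shift is small against the confidence interval.

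**What to change.** In SAP 4.2.2 and the matching protocol section, remove the follow-up criterion and define PP by treatment received and absence of major protocol deviations. Then state in notes to Tables 1.1b and 11b that PP follows the ITT rules, on one day count:

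- the event-or-adequate-follow-up denominator for the exact CI;
- the Kaplan-Meier estimate, with event-free withdrawals and non-cardiac deaths kept in the set as censored subjects.

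The PP proportion will then share whatever upward error early loss causes in the ITT proportion, so the two are comparable, and the Kaplan-Meier estimate is there to allow for it.

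Adding only a clause admitting subjects with a TVF event within 3 years is second best. It restores the cardiac deaths but shuts event-free withdrawals out of both the proportion and the Kaplan-Meier estimate, which would have almost no early censoring left to correct with. By step 6 that overstates TVF by about 2.0-2.7 points at 7% yearly loss, or 0.3-0.4 point at 6% over 5 years.

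The cost is a wording change in two places and two table notes, with no new data. The protocol section is 12.4.2 in the supplied v1.2; the SAP cites protocol Version 3.0, which was not supplied, so the current text should be checked.

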4.3 Methods of Analyses

Descriptive statistics will be used to present the data and to summarize the results. Categorical variables will be presented using counts and percentages. Proportions will be calculated using known non-missing values. Continuous variables will be summarized by presenting the number of observations (N), mean, two-sided 95% confidence interval of the mean, standard deviation,

median, minimum and maximum values. Unless otherwise indicated, all statistical tests and/or confidence intervals will be performed at $\alpha = 0.05$ (two-sided).

For adverse event reporting, which includes the primary and secondary safety endpoints, the primary analysis will be based on subject counts, not event counts. A subject with more than one event will be counted only once toward the event rate based on the total number of subjects with adverse events. Additionally, an event rate based on event counts will also be presented in the adverse event tables. Unless specified otherwise, statistical significance will be declared if the two-sided p-value is < 0.05 .

All statistical analyses will be performed using Statistical Analysis System (SAS) for Windows (version 9.4 or higher, SAS Institute Inc. Cary, NC) or other widely accepted statistical or graphical software. In general, data for all study subjects will be combined and presented. Individual data will be presented in subject listings.

